## 420 **13. Multiple Comparisons/Multiplicity**

421 For the co-primary analyses, the intervention will be deemed effective only if the null hypotheses  
422 for both co-primary outcomes are rejected. Therefore, the type I error rate is not inflated and  
423 there will be no correction for multiple comparisons.

424 For the secondary analyses, the false discovery rate will be controlled using the adaptive Two  
425 Stage Benjamini-Hochberg procedure. False discovery rate corrections will be applied within  
426 each of the following categories:

- 427 • Secondary CGM Analyses
  - 428 ○ Over the full 24 hours of the day
  - 429 ○ During the daytime, nighttime, or post-meal periods
- 430 • Secondary Insulin Analyses, HbA1c Analyses, and Clinical Metrics
- 431 • Questionnaires
- 432 • Subgroup Analyses
  - 433 ○ Based on baseline factors
    - 434 ■ For the hyperglycemic outcome
    - 435 ■ For the hypoglycemic outcome
  - 436 ○ Within the 14-<21 age group
    - 437 ■ CGM Metrics
      - 438 • Over the full 24 hours of the day
      - 439 • During the daytime, nighttime, or post-meal periods
    - 440 ■ Insulin Metrics, HbA1c Metrics, and Clinical Metrics
  - 441 ○ Within the 21-<30 age group
    - 442 ■ CGM Metrics
      - 443 • Over the full 24 hours of the day

444                     • During the daytime, nighttime, or post-meal periods  
445                     ▪ Insulin Metrics, HbA1c Metrics, or Clinical Metrics  
446     ○ Within the HbA1c  $\leq 8.5\%$  group  
447                     ▪ CGM Metrics  
448                     • Over the full 24 hours of the day  
449                     • During the daytime, nighttime, or post-meal periods  
450                     ▪ Insulin Metrics, HbA1c Metrics, or Clinical Metrics  
451     ○ Within the HbA1c  $\geq 8.6\%$  group  
452                     ▪ CGM Metrics  
453                     • Over the full 24 hours of the day  
454                     • During the daytime, nighttime, or post-meal periods  
455                     ▪ Insulin Metrics, HbA1c Metrics, or Clinical Metrics

456     A table containing the number of p-values broken down into each of these categories will also be  
457     provided.

458     For safety analyses, the per-protocol analysis, tests for carryover effects, and intervention  
459     compliance analyses, no adjustments for multiple comparisons will be made. For the replication  
460     of the primary analyses omitting the first four weeks of each period (overall and within the age  
461     and HbA1c groups), the p-values will be included in the appropriate daytime, nighttime, and  
462     post-meal CGM category.

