### 1579 10.3 Sample Size

1580 The sample size calculation is detailed in a separate document and summarized below.

1581 For computing sample size, estimates of the standard deviation (SD) for time spent in  
1582 hypoglycemia and hyperglycemia were made based on data from previous studies, Medtronic  
1583 670G Pivotal Trial, DIAMOND, JDRF CGM RCT, and REPLACE-BG.

1584

1585 Analyses of both primary outcomes must have a significant result ( $p < 0.05$ ) to declare benefit of  
1586 the intervention. The two co-primary outcomes therefore do not inflate the type 1 error, but  
1587 requiring both to be significant can inflate the type 2 error. A Bonferroni correction was  
1588 therefore applied to the power calculations by adding the type 2 error rate (i.e., 100% minus  
1589 power) for the two analyses. This represents a conservative estimate for composite power as the  
1590 probability that both tests will reject the null hypothesis.

1591

1592 The total sample size was computed to be 65 for the following assumptions (1) 90% power, with  
1593 adjustment to account for the two co-primary analyses, (2) a 5% absolute reduction in time  $>180$   
1594 mg/dL (10.0 mmol/L) with a standard deviation of paired differences of 12%, and a 2-sided type  
1595 1 error rate of 5%, and (3) a non-inferiority limit of 2% for the treatment group comparison of  
1596 time  $<54$  mg/dL (3.0 mmol/L) with an SD of paired differences of 1.3% and 1-sided type 1 error  
1597 of 2.5%.

1598  
1599 A sample size of 100 completing the trial has been selected to provide increased precision for  
1600 safety analyses and subgroup analyses. With a sample size of 100 participants completing the  
1601 crossover trial, the primary analysis will have 98% power.

1602  
1603 **10.4 Outcome Measures**

1604 All CGM derived indices will be calculated over the first 84 days of each period. The beginning  
1605 of the period is defined as the time that auto mode is first turned on, which per protocol is 6-10  
1606 days after the period starts. A post-meal period is defined as follows: meal starts at the time the  
1607 carbohydrate is entered and post-meal period ends at three hours after a meal unless another  
1608 carbohydrate is entered  $<3$  hours, which is then considered the end of the post-meal period.

1609  
1610 Hypoglycemia metrics are considered both safety and efficacy outcomes.

1611  

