18   phase may vary depending on the participant's comfortability using the devices.

19   **2. Statistical Hypotheses**

20   In this study, there are two co-primary outcomes:

- 21   • Superiority in the percentage of time spent with sensor glucose levels above 180 mg/dL  
22   during the daytime (6:00 AM to 11:59 PM)
- 23   • Non-inferiority in the percentage of time spent with sensor glucose levels below 54  
24   mg/dL calculated over the full 24 hours of the day, with a non-inferiority limit of 2%  
25   based on clinical judgment.

26   Separate analyses will be performed for each co-primary outcome, and both analyses must  
27   produce a statistically significant result in order to declare benefit of the intervention.

28   For each of these analyses, the two corresponding pairs of null and alternative hypotheses are as  
29   follows:

30   Hyperglycemic Outcome:

- 31   • *Null Hypothesis:* There is no difference in the percentage of time spent with sensor  
32   glucose levels above 180 mg/dL between the two treatments during the daytime for the  
33   entire study population.
- 34   • *Alternative Hypothesis:* There is a nonzero difference in the percentage of time spent  
35   with sensor glucose levels above 180 mg/dL between the two treatments during the  
36   daytime for the entire study population.

37   Hypoglycemic Outcome:

38     • *Null Hypothesis*: There is a mean difference of at least 2% in the percentage of time spent  
39       with sensor glucose levels below 54 mg/dL between the AHCL system and the 670G  
40       system over the full 24 hours of the day for the entire study population.  
41     • *Alternative Hypothesis*: There is a mean difference of less than 2% in the percentage of  
42       time spent with sensor glucose levels below 54 mg/dL between the AHCL system and the  
43       670G system over the full 24 hours of the day for the entire study population.

44     **3. Sample Size**

45     The sample size calculation for this study is detailed in a separate document (in addition to the  
46       protocol) and summarized below. Sample size was calculated based on the following  
47       assumptions:

48     • 90% power  
49     • 5% true absolute reduction in percent time > 180 mg/dL during the daytime with a  
50       standard deviation of paired differences of 12% and a two-sided Type 1 error rate of 5%  
51     • Non-inferiority limit of 2% for the treatment group comparison of percent time < 54  

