52       mg/dL with a standard deviation of paired differences of 1.3% and a one-sided Type 1  
53       error rate of 2.5%

54     In the sample size calculation, an adjustment was made to account for the two co-primary  
55       analyses. Analyses of both primary outcomes must have a significant result ( $p < 0.05$ ) to declare  
56       benefit of the intervention. The two co-primary outcomes therefore do not inflate the Type 1  
57       error, but requiring both to be significant can inflate the Type 2 error. Therefore, a Bonferroni  
58       correction was applied to the power calculations by adding the Type 2 error rate (i.e., 100%  
59       minus power) for the two analyses. This represents a conservative estimate for composite power  
60       as the probability that both tests will reject the null hypothesis.

61     With the above assumptions, sample size was calculated to be 65. For entry into the trial, this  
62       was increased to 112 to provide greater precision for the primary and secondary analyses.

63     **4. Outcome Measures**

64     **Co-Primary Efficacy Endpoints\*:**

65     1) Percentage of daytime (6:00 AM to 11:59 PM) spent with sensor glucose levels above  
66       180 mg/dL (superiority)  
67     2) Percentage of time spent with sensor glucose levels below 54 mg/dL over the full 24  
68       hours of the day (non-inferiority)

69     \*Both co-primary efficacy endpoints are calculated over each treatment period for the full 24  
70       hours, daytime (6:00 AM – 11:59 PM), and nighttime (12:00 AM – 5:59 AM). They are also  
71       calculated for each post-meal period measured for up to three hours after the start of a meal.

72     **Secondary Efficacy Endpoints:**

73     **CGM Metrics**

74       **Overall Glucose Control**

75       1) Mean glucose  
76       2) Time in range 70 and 180 mg/dL

77 3) Time in range 70 and 140 mg/dL

78 *Hyperglycemic Outcomes*

79 4) Time above 180 (daytime is a co-primary outcome) and 250 mg/dL

80 5) Peak glucose and change from baseline to the peak (only calculated for post-meal  
81 periods)

82 *Hypoglycemic Outcomes*

83 6) Time below 54 (over 24 hours is a co-primary outcome) and 70 mg/dL

84 *Glycemic Variability*

85 7) Coefficient of variation

86 Insulin Delivery Metrics

87 8) Total Daily Insulin Units

88 9) Basal Daily Insulin Units

89 10) Bolus Daily Insulin Units

90 11) Total Daily Insulin Units per Kilogram of Weight

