91 12) Total Basal Insulin Units per Kilogram of Weight

92 13) Total Bolus Insulin Units per Kilogram of Weight

93 HbA1c Metrics

94 14) HbA1c

95 Clinical Metrics

96 15) BMI

97 Additional Exploratory Endpoints:

98 CGM Metrics:

99 *Continuous Outcomes:*

100 1) Time below 50 and 60 mg/dL

101 2) Time above 300 mg/dL

102 3) Area under the curve of sensor glucose levels above 180 mg/dL

103 4) Area over the curve of sensor glucose levels below 70 mg/dL

104 5) Standard deviation of sensor glucose levels

105 *Binary Outcome:*

106 1) Time in range (70-180 mg/dL) >70% and time below 54 mg/dL <1%.

107 HbA1c Metrics:

108 *Binary Outcomes:*

109 1) Improvement in HbA1c  $\geq 0.5\%$

110 2) Improvement in HbA1c  $\geq 1.0\%$

111 3) Relative reduction in HbA1c  $\geq 10\%$

112 4) HbA1c  $< 7.0\%$

113 All secondary efficacy and exploratory CGM metrics will be calculated over each treatment  
114 period for the full 24 hours, daytime (6:00 AM – 11:59 PM), and nighttime (12:00 AM – 5:59  
115 AM). They also will be calculated for each post-meal period measured for up to three hours after  
116 the start of a meal. The same will be done for all secondary efficacy insulin endpoints. It is

117 important to note that all hypoglycemic outcomes are considered both efficacy and safety  
118 outcomes.

119 **4.1 Calculation of the Co-Primary Outcomes**

120 As noted above, the co-primary outcomes are:

121 • Daytime Hyperglycemia (percent CGM readings above 180 mg/dL)  
122 • Hypoglycemia (percent CGM readings below 54 mg/dL; daytime/nighttime combined)

123 For each co-primary outcome, a single value will be calculated for each subject for each period  
124 by pooling all CGM readings in the first 84 days of each period or up to and including the 12-  
125 week visit date (whichever comes first).

126 In these calculations, each period will start at the time that the subject turns on auto mode. If the  
127 exact time is not known, then the period will start at midnight the day after the subject initiates it.  
128 We expect auto mode to be initiated 6-10 days after the randomization visit in period 1 and 6-10  
129 days after the first day of period 2. Participants who are 670G auto mode users at screening may  
130 initiate auto mode at the beginning of a study period in which the 670 3.0 HCL pump is being  
131 used. The end of the period will be defined as either 11:59 PM on the 12-week visit date or  

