### 285 **7.2 Secondary Insulin Outcomes**

286 For each secondary insulin outcome, mean  $\pm$  SD or summary statistics appropriate to the  
287 distribution will be reported by treatment arm. All secondary insulin metrics calculated over the  
288 full 24 hours of the day, daytime, and nighttime will be compared between treatment arms using  
289 the same repeated measures least squares regression model described above for the co-primary  
290 outcomes.

291 The insulin outcomes listed in Section 4 under “Additional Exploratory Endpoints” will be  
292 tabulated separately by treatment arm with no formal statistical comparison. For these outcomes,  
293 change will be calculated from the start of the period.

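### Does the adaptive FDR procedure in SAP section 13 need a limit on the raw p-value, because it can call a secondary result significant at raw p above 0.05?

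*SAP*

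**What the plan says.** SAP section 13: "For the secondary analyses, the false discovery rate will be controlled using the adaptive Two" Stage Benjamini-Hochberg procedure. The correction is made separately within each listed family. The section states neither the FDR level nor the variant. Protocol 10.13 names the same procedure and puts the significance threshold below 0.05. For an FDR method this is naturally read as the FDR level, that is, the limit for the adjusted p-value. Neither document sets a separate condition on the raw p-value.

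Two families matter here.

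- **24-hour CGM.** SAP section 4 lists mean glucose, time 70-180, time 70-140, time >180, time >250, coefficient of variation (CV) and, under hypoglycemia, "Time below 54 (over 24 hours is a co-primary outcome) and 70 mg/dL". With 24-hour time <54 taken out as co-primary, seven tests remain. Six remain if time <70 is handled only as a safety outcome. SAP section 4 says it is "important to note that all hypoglycemic outcomes are considered both efficacy and safety" outcomes, and section 13 exempts some analyses from adjustment in a sentence that opens "For safety analyses, the per-protocol analysis, tests for carryover effects, and intervention".
- **"Secondary Insulin Analyses, HbA1c Analyses, and Clinical Metrics".** SAP section 7.2 compares six insulin metrics over the "full 24 hours of the day, daytime, and nighttime will be compared between treatment arms using" the primary model. That is 18 tests, or 24 with the post-meal window from section 4. HbA1c and BMI bring the family to 20 or 26.

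Benefit is declared only if both co-primary null hypotheses are rejected. Those two tests carry no FDR correction.

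**The concern.** Many readers take 0.05 as an upper limit for any p-value called significant. Ordinary Benjamini-Hochberg at 0.05 respects that limit, because its last and largest step is 0.05 itself. The two-stage version does not: it first estimates how many tests reflect real effects, then relaxes its level accordingly.

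Five of the seven 24-hour CGM metrics are closely related measures of overall glucose and hyperglycemia. If AHCL works they will tend to be rejected together, which loosens the cutoff for CV and time <70 mg/dL, two outcomes that answer different questions. Either could then be labelled significant at a raw p of 0.08 to 0.14, with an unadjusted 95% confidence interval that includes no difference. At stake is the wording of secondary and subgroup results.

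**Working it through.** **Inputs.** The FDR level q = 0.05 comes from Protocol 10.13. Family sizes are counted from SAP sections 4, 7.2 and 13. The planning effect is from SAP section 3: "5% true absolute reduction in percent time > 180 mg/dL during the daytime with a" standard deviation of paired differences of 12%. The number of completers is from Protocol 10.3: "A sample size of 100 completing the trial has been selected to provide increased precision for" safety and subgroup analyses.

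**The plan's own figures.** The documents give no raw-p cutoff to reproduce. The planning effect can be checked against the stated power. A paired t-test with 5%, SD 12% and n = 100, combined with the non-inferiority test (margin 2%, SD 1.3%), gives 98.5% composite power against the stated 98%. The smallest n for 90% is 63, against the stated 65.

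**Cutoffs.** Stage 1 is Benjamini-Hochberg at a = q/(1+q) = 0.05/1.05 = 0.0476, giving r rejections among m tests. Stage 2 is Benjamini-Hochberg at a·m/(m−r). One further isolated test is then rejected when p ≤ (r+1)·a/(m−r).

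| m | r | Formula | Cutoff |
|---|---|---|---|
| 7 | 3 | 4 × 0.0476 / 4 | 0.048 |
| 7 | 4 | 5 × 0.0476 / 3 | 0.079 |
| 7 | 5 | 6 × 0.0476 / 2 | 0.143 |
| 6 | 3 | 4 × 0.0476 / 3 | 0.063 |
| 6 | 4 | 5 × 0.0476 / 2 | 0.119 |
| 6 | 5 | 6 × 0.0476 / 1 | 0.286 |
| 26 | 13 | 14 × 0.0476 / 13 | 0.051 |
| 20 | 10 | 11 × 0.0476 / 10 | 0.052 |

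The variant that uses a = 0.05 gives slightly larger values (0.083 in place of 0.079).

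For an isolated test the crossing comes at half the family when m is even and just over half when m is odd. HbA1c and BMI count toward the number in their family. Clustered p-values can cross earlier: with .001, .002, .003, .045, .055, .06 and .8, stage 1 rejects three and the procedure finally rejects six. So raw p above 0.05 can indeed be called significant.

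**Is the promised error rate kept?** Take m = 7 with six overwhelming true effects and one null. The null is rejected when p ≤ 7 × 0.0476 / 1 = 0.333. It is then one false rejection among seven, so FDR = 0.333/7 = 0.048. Under ordinary Benjamini-Hochberg, or with a cap at 0.05, the same null is rejected with probability 0.05 and FDR = 0.05/7 = 0.007. The wide cutoff is what brings the FDR back up to its nominal level.

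Simulation agrees. With four, five or six overwhelming true effects among seven and independent nulls, the FDR is 4.86%, 4.90% and 4.84%. For correlated tests, five metrics were given the planning effect, z = 5/(12/√100) = 4.17, or a weaker z = 2.8. Their pairwise correlations were 0.5 or 0.8, and the null tests were correlated 0 or 0.4 with them. The FDR again stayed below 5%. With the cap it was at most 1.7%.

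**The per-test rate.** At z = 4.17 a truly null CV is called significant in about 15% of runs (m = 7) or 27% (m = 6). At z = 2.8 the figures are 10% and 18-19%. With the cap they are at most 5%, but that holds by construction.

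**Price of a cap (m = 7, other metrics at z = 4.17).** Power for a true CV difference falls from 91% to 80% when its z is 2.8, and from 70% to 51% when its z is 2.

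**The case for a change.** The strongest argument for acting is that CV and time <70 mg/dL are not further views of hyperglycemia, yet they gain a looser cutoff from the success of five correlated hyperglycemia metrics. A truly null CV could be called significant in 15% to 27% of trials. About 67% (m = 7) or 82% (m = 6) of those calls would have raw p of 0.05 or more. One added sentence would prevent this at no cost in data or models.

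The arithmetic stands. The inference does not, for three reasons.

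- The 15% and 27% are false-positive rates for one null test in a family full of real effects. The SAP never undertook to hold that rate at 5%; it chose the expected share of false claims among all claims.
- The rates assume that all five metrics share the standardized effect planned for daytime time >180 alone. The documents give no planning effect for the other four. At z = 2.8 all five are rejected in only 58-67% of runs.
- The added sentence has a cost: it loses power, and it would remove the significance label from an unfavourable difference in time <70 mg/dL, an outcome the SAP also treats as safety.

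Two small points remain. SAP section 13 leaves the FDR level to the protocol and does not name the variant. Time <70 could be counted inside or outside the family. Both affect the exact cutoff; neither breaks the FDR control. Printing raw p-values beside adjusted ones would meet the reader's interest without changing any decision rule.

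**Conclusion.** The concern does not hold. A raw p above 0.05 among the rejected tests is a known and intended property of an adaptive FDR procedure. The property the plan claims, FDR control at 5% within each family, is met: at most 4.9% in the scenarios examined. No stated number or rule is wrong.

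A cap would swap that error rate for a per-test rate the plan did not choose. The FDR would fall to 1.7% or less, and power for a true CV effect would drop by 11 to 19 percentage points (91 − 80 and 70 − 51). Reasonable statisticians can differ on that trade. The co-primary conclusions are unaffected and subgroup results are already labelled exploratory.

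This rests on reading the protocol's 0.05 as the FDR level, on family sizes counted from the SAP, and on simulation for correlated tests. If the protocol's 0.05 were meant as a raw-p limit, the issue would not arise at all.

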1792 • Age: as a continuous variable and in two age groups: 14- $<$ 21 and 21- $<$ 30 years old  
1793 • Baseline HbA1c: as a continuous variable and in two groups: HbA1c  $\leq$ 8.5% and  $\geq$ 8.6%  
1794 • Insulin method/CGM: 670G user, injection user with CGM, injection user without CGM,  
1795 pump user with CGM, pump user without CGM  
1796 • T1D duration as a continuous variable  
1797 • Sex  
1798 • Race/ethnicity  
1799 • Random C-peptide level  
1800 Beyond above assessment for interactions, the primary and secondary analyses also will also be  
1801 conducted separately in the two age groups and the two HbA1c groups, in addition to the CGM  
1802 metrics considered as safety outcomes. Analyses will only be replicated within these subgroups  
1803 for efficacy outcomes where p-values are being computed.  
1804  
1805 **10.13 Multiple Comparison/Multiplicity**  
1806 For the primary analyses, the intervention will be deemed effective only if the null hypotheses  
1807 for both co-primary outcomes are rejected. The type 1 error is therefore not inflated and there  
1808 will be no correction for multiple comparisons.  
1809  
1810 For the secondary analyses, the false discovery rate will be controlled using the adaptive Two  
1811 Stage Benjamini-Hochberg procedure with  $<$ 0.05 as the threshold for statistical significance.  
1812  
1813 **10.14 Additional Tabulations and Analyses**  
1814 **10.14.1 Device Issues and Tabulations**  
1815 All reported device issues will be tabulated regardless of whether they were associated with  
1816 adverse events.  
1817  
1818 Detailed tabulations will include frequency of use of the system, discontinuation rate, and reasons  
1819 for discontinuation.  
1820  
1821 The amount of auto mode system use and CGM use will be calculated over each treatment  
1822 period. Similar repeated measures least squares regression models as described for the co-  
1823 primary outcomes will be used to compare the percentage of time of CGM use and auto mode

1824 use between the two periods. Monthly values for auto mode use and CGM use also will be  
1825 reported.

1826

1827 **10.14.2 Analysis of Quality of Life Data**

1828 Quality of life data collected during study assessments will be scored based on established  
1829 procedures and descriptive statistics (e.g., mean, range) will be calculated for each questionnaire  
1830 at each time point and across treatment groups. Similar models as described above for the  

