132 exactly 2,016 hours (i.e. 24 hours/day\*84 days) after auto mode is turned on, whichever comes  
133 first. If the exact time that auto mode is turned on is unknown, then it will be defined as 11:59  
134 PM on the 12-week visit date or 11:59 PM on the 84th day of the period, whichever comes first.  
135 Data will not be truncated due to protocol deviations.

136 CGM readings will be used according to the time of day as follows:

137 *Hyperglycemic Outcome*

138 CGM readings will be limited to daytime values (between 6:00 AM and 11:59 PM, inclusively).

139 *Hypoglycemic Outcome*

140 All CGM readings will be used with no restriction according to time of day (i.e., all 24 hours).

141 The baseline value of each co-primary outcome will be calculated by pooling all CGM readings  
142 from the last 14 days of the CGM run-in phase. As mentioned above, only readings occurring  
143 between 6:00 AM and 11:59 PM (inclusively) during this period will be included in the  
144 calculation of the hyperglycemic outcome. If less than 336 hours of CGM data are available  
145 during this period, then an additional preceding day will be pooled one at a time until either 336  
146 hours are available or 30 total days are reached (whichever comes first).

147 **4.1.1 Replication of Co-Primary Analyses Omitting the First Four Weeks of Each Period**

148 The co-primary analyses will be replicated after omitting the first four weeks of each crossover  
149 period. In these analyses, the first and last day of each crossover period will be the same as  
150 defined above. Therefore, each period in these analyses will start exactly 672 hours (i.e. 24  
151 hours/day\*28 days) after the start of the period as defined above. For each co-primary outcome  
152 metric, a single value will be calculated by pooling all CGM data from this starting point to the  
153 final day of the period, inclusively. Only daytime data (6:00 AM to 11:59 PM) will be included  
154 in the calculation of the hyperglycemic outcome.

155 Other than the differences described above, replication of co-primary analyses omitting the first  
156 four weeks of each period will be the same as the main analyses.

157 **4.2 Calculation of Secondary Outcomes**

158 All secondary CGM metrics calculated over the full 24 hours of the day will be computed  
159 analogously as described above for the primary analysis. Baseline CGM metrics will also be  

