## 273 **7. Analysis of the Secondary Endpoints**

### 274 **7.1 Secondary CGM Outcomes**

275 For each secondary CGM outcome, mean  $\pm$  SD or summary statistics appropriate to the  
276 distribution will be reported by treatment arm. All secondary CGM metrics calculated over the  
277 full 24 hours of the day, daytime, and nighttime will be compared between treatment arms using  
278 the same repeated measures least squares regression model described above for the co-primary  
279 outcomes.

280 Replication of the primary outcome omitting the first four weeks of each period (as described in  
281 section 4.1.1) will be considered a secondary analysis. In this analysis, the baseline value  
282 included in the model will be the same baseline value as in the primary analysis.

283 The CGM outcomes listed in Section 4 under "Additional Exploratory Endpoints" will be  
284 tabulated separately by treatment arm with no formal statistical comparison.

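### SAP section 13 files the four-week-omitted hypoglycemia replicate, a 24-hour metric, in the daytime/nighttime/post-meal FDR family. If its p-value tests the 2% margin, a near-certain rejection can loosen the cut-offs for the other tests there.

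*SAP*

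**What the plan says.** SAP 4.1 defines the hypoglycemia co-primary, percent time below 54 mg/dL, without a time-of-day limit: "All CGM readings will be used with no restriction according to time of day (i.e., all 24 hours". SAP 4.1.1 repeats both co-primary analyses without the first four weeks of each period and says that, apart from the window, replication omitting the first "four weeks of each period will be the same as the main analyses". SAP 7.1 makes this a secondary analysis: "Replication of the primary outcome omitting the first four weeks of each period (as described in" section 4.1.1) is classed there as secondary.

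SAP 13 then states: "For the secondary analyses, the false discovery rate will be controlled using the adaptive Two" Stage Benjamini-Hochberg procedure, applied within listed categories. The secondary CGM tests form two categories, "Over the full 24 hours of the day" and "During the daytime, nighttime, or post-meal periods". The same pair is repeated within each of two age groups and two HbA1c groups. For the replication, overall and in the age "and HbA1c groups), the p-values will be included in the appropriate daytime, nighttime, and" post-meal CGM category. No 24-hour destination is offered. SAP 13 gives no FDR level. Protocol 10.13 does, setting a value below 0.05 "as the threshold for statistical significance".

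SAP 6.2.2 judges non-inferiority by comparing the upper 95% confidence limit with 2%. It then adds a two-sided p-value at the 5% level without naming its null.

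**The concern.** Of the two replicates, only the daytime hyperglycemia one belongs in the daytime/nighttime/post-meal category. The hypoglycemia replicate is a 24-hour metric, and the SAP has a 24-hour category.

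The placement may also have a numerical effect. Benjamini-Hochberg cut-offs rise with the number of rejections in the family. If the p-value entered is for the 2% margin, the plan's own inputs make rejection close to certain. That rejection says nothing about superiority, yet it would make every superiority test in the family easier to pass. At stake is how far the secondary daytime, nighttime and post-meal claims can be trusted, and the same claims in four subgroup families.

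**Working it through.** **Inputs.** From SAP 3: margin 2%, SD of paired differences 1.3% (time below 54), one-sided alpha 2.5%; effect 5%, SD 12% (daytime time above 180), two-sided alpha 5%; composite power 90%; N = 65. From Protocol 10.3: 98% power at 100 completers. From Protocol 10.13: FDR level 0.05.

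**The plan's own figure.** Paired t-test power, with composite power = 1 − (β1 + β2), first reaches 90% at N = 63, close to the stated 65. It is 91.1% at 65 and 98.5% at 100 (stated: 98%). The inputs are therefore read correctly.

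**Is rejection of the margin near certain?** z = (2 − true difference) / (1.3/√n).
- n = 100, true difference 0: 2/0.13 = 15.4.
- n = 100, true difference 1%: 1/0.13 = 7.7.
- n = 100, true difference 0, SD doubled to 2.6%: 2/0.26 = 7.7.
- n = 25 (assumed subgroup size), true difference 0: 2/0.26 = 7.7, power above 99.99%. At a true difference of 1%, power is 95.8%.

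The 12-week SD is applied to the 8-week replicate. The doubled-SD line shows that this assumption is not critical.

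**Family size (a count; the SAP gives none).** SAP 4 lists eight CGM metrics per window: mean glucose, time 70–180, time 70–140, time above 180, above 250, below 54, below 70, and coefficient of variation. Daytime 8 − 1 (co-primary) = 7; nighttime 8; post-meal 8 + 2 peak metrics = 10. The total is 25, plus the two replicates.

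**Mechanism, in plain Benjamini-Hochberg terms.** With 25 tests, the smallest p-value meets a cut-off of 0.05 × 1/25 = 0.0020. Add one sure rejection and it ranks second of 26: 0.05 × 2/26 = 0.0038, nearly double.

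**Simulation of the two-stage procedure at 0.05.** Test statistics are equicorrelated normal and true effects are 3.5 standard errors. FDR among the other tests leaves the hypoglycemia replicate out of both numerator and denominator. Ranges span two common forms of the procedure.

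| 25 other tests | Without replicate | With margin p-value |
|---|---|---|
| all null, independent | 4.8–5.1% | 9.2–9.7% |
| all null, correlation 0.5 | 3.7–3.9% | 6.4–6.6% |
| all null, correlation 0.8 | 2.2–2.4% | 3.4–3.5% |
| 3 true effects, independent | 4.6–4.9% | 6.0–6.3% |
| 12 true effects, independent | 4.4–4.6% | 4.8–5.1% |
| 20 true effects, independent | 3.8–4.1% | 4.0–4.3% |

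The daytime hyperglycemia replicate rightly sits in this family, and at the planned effect it has z = 5/(12/√100) = 4.17, itself close to a sure rejection. Including it as a true effect gives:

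| Other true effects | Correlation 0 | 0.5 | 0.8 |
|---|---|---|---|
| 4, without → with | 4.6 → 5.4% | 4.2 → 5.0% | 2.9 → 3.6% |
| 8, without → with | 4.5 → 5.0% | 4.2 → 4.9% | 3.0 → 3.6% |
| 12, without → with | 4.5 → 4.7% | 4.2 → 4.7% | 2.9 → 3.7% |
| none, with | 7.2% | 5.6% | 3.3% |

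FDR over the whole declared family, replicate included, stays at or below about 5% throughout. Simulation error is one or two tenths of a point.

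**Would the 24-hour family be a better home for a margin p-value?** No. That family has 8 − 1 = 7 other tests, and at the global null with independence their FDR becomes 9.0–9.5%.

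**The case against.** A reader might infer that the plan's FDR control at 5% fails. The documents do not support that. SAP 13 promises control within each declared category, and over that category the rate stays at or below about 5%. The rate that rises is for a subset of the category, which the plan never undertook to control separately.

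A reader might also take 9% as the expected size. That figure needs every other test to be null and independent. The plan itself assumes a 5-point fall in daytime time above 180, and daytime mean glucose, time in range and time above 250 come from the same readings. With the hyperglycemia replicate included and four or more other true effects, the rate is at most about 5.4%, and below 4% at correlation 0.8.

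The mechanism also depends on which null is tested. SAP 6.2.2 rests non-inferiority on the confidence limit and foresees superiority or inferiority conclusions from the same interval, so a zero-difference p-value is a possible reading. Under it there is no free rejection and only the misfiling remains. On the other side, the only null hypothesis in SAP 2 for this outcome is a difference of at least 2%, and SAP 3 requires a significant p-value for both co-primaries. The text does not settle the matter.

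These limits stand. They shrink the numerical consequence but leave two facts: a 24-hour test in a family for other windows, and a p-value with no stated null. The word "appropriate" in the rule does not help, because the rule names only the daytime, nighttime and post-meal category.

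**Conclusion.** The concern holds in limited form. The misfiling is certain from the text and recurs in four subgroup families. Its effect on error rates is conditional. If the p-value tests the margin, the FDR among the other tests rises: to about 9% at worst (all null, independent), to about 5.0–5.4% with a few true effects and correlation of 0 to 0.5, and not materially above 5% with high correlation or many true effects. If it tests zero difference, there is no such inflation.

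The co-primary decision is unaffected, since it needs both nulls rejected without correction. Only secondary tests and exploratory subgroup tests are touched. The sizes rest on a count of 25 other tests, equicorrelated normal statistics, effects of 3.5 standard errors and the planned SD of 1.3%. Subgroup power also assumes 25 participants per group.

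**What to change.** In SAP 6.2.2, state which null the hypoglycemia p-value tests. In SAP 13:
- Report the four-week-omitted hypoglycemia replicate as a confidence interval against 2%, as an unadjusted sensitivity analysis outside every FDR family. The SAP already leaves the per-protocol analysis of the same outcomes unadjusted.
- Do not move a margin p-value to the 24-hour family, where it would have the same effect.
- If a zero-difference p-value is also reported, place it in the 24-hour family.
- Keep only the daytime hyperglycemia replicate in the daytime/nighttime/post-meal family.
- Apply the same rule in the two age and two HbA1c groups.

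The cost is a sentence or two of SAP text and slightly stricter cut-offs for the remaining tests. No data collection changes.
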